 - For cohorts 1 to 9, hyperglycemia, peripheral neuropathy, dry eye, corneal disorders and blurred vision, skin reactions, and infusion related reactions are considered adverse events of special interest (AESI) for enfortumab vedotin. These are medical concepts of composite terms based on the search criteria utilizing MedDRA terminology (standard MedDRA query [SMQ], sponsor specific query [SSQ], customized MedDRA query [CMQ], high level group term [HLGT], high level term [HLT], preferred term [PT]). Other AEs may be added as AESI as necessary due to ongoing pharmacovigilance activities. The search criteria for AESI will be maintained in a separate document and finalized prior to database lock.
 - For selected AESI, time to onset of AESI will be calculated. Time to first onset of a specific AESI will be calculated as the time from the first dose of study drug to the onset of the first treatment-emergent adverse event that meets the respective search criteria.

- For selected AESI, time to resolution of AESI will be calculated. Resolution is defined as event outcome of ‘recovered/resolved’ or ‘recovered/resolved with sequelae’. For treatment-emergent events with an outcome of ‘recovered/resolved’ or ‘recovered/resolved with sequelae’, time to resolution will be calculated as time from the event onset date to end date.

Time to resolution is defined at the event level. AE records that belong to the same event will be linked.

- Other AEs of risk for enfortumab vedotin
For cohorts 1 to 9, pneumonitis/interstitial lung disease (ILD) is defined as other AEs of risk for EV. Similar as AESI, terms are based on the search criteria utilizing MedDRA terminology.
- Adverse events of special interest for pembrolizumab (AEOSI)
 - For cohort 9, AEOSI are immune-mediated events and infusion-related reactions, following the Keytruda AEOSI List which is a pre-specified list of preferred terms (PTs) developed by MSD to consistently characterize the nature and frequency of each AEOSI across the clinical program, regardless of causality as reported by investigators. These PTs are considered to be medically equivalent to the identified risks for pembrolizumab. The list of PTs may be updated by MSD based on emerging pembrolizumab safety data or as a result of MedDRA updates.
- Clinical laboratory variables

Below is a table of the laboratory tests that will be performed during the conduct of the study.

Panel/Assessments	Parameters to be Analyzed	NCI-CTCAE Grading (Hyper/Hypo)

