6 STATISTICAL METHODOLOGY

6.1 General Considerations

Continuous data will be summarized descriptively including the number of subjects (n), mean, standard deviation (SD), median, minimum and maximum. When needed, the use of other percentiles (e.g., 10%, 25%, 75%, 90%) will be specified in the relevant section. In addition, for plasma (MMAE) and serum concentrations, the coefficient of variation, the geometric mean and the coefficient of variation for geometric mean will also be calculated. Categorical data will be summarized by frequencies and percentages. Percentages by categories will be based on the number of subjects with no missing data, i.e., the percentages for the nonmissing categories will add up to 100%.

Unless otherwise specified, confidence intervals (CIs) will be calculated at two-sided 95% level. For time-to-event endpoints, median survival time will be estimated using Kaplan-Meier method, with 2-sided 95% CI.

Baseline value is defined as the last nonmissing measurement prior to the first dose of study drug unless specified otherwise. In general, data will be summarized by cohort and overall.

All data summarization and analyses will be performed using SAS® Version 9.4 or higher on Red Hat Enterprise Linux. Specifications for table, figures, and data listing formats can be found in the TLF specifications.

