The number and percentage of subjects with TEAEs, as classified by SOC and PT will be summarized by NCI-CTCAE grade and by relationship to study drug. If a subject has multiple TEAEs with the same SOC or PT, but with differing CTCAE grade or relationship, then the subject will be counted once with the worst nonmissing CTCAE grade and the highest degree of relationship. If CTCAE grade is missing for all episodes of the event, the subject will be counted under missing CTCAE grade. If relationship is missing for an adverse event, it's considered to have the highest degree of relationship.

The number and percentage of subjects with treatment-emergent AESIs, as classified by AESI category and PT, will be summarized for each cohort and overall for the following:

- Treatment-emergent AESIs,
- Drug-related treatment-emergent AESIs,
- Treatment-emergent AESIs by NCI-CTCAE grade,
- Drug-related treatment-emergent AESIs by NCI-CTCAE grade,

- Serious treatment-emergent AESIs,
- Treatment-emergent AESIs leading to permanent discontinuation of study drug,
- Treatment-emergent AESIs leading to permanent discontinuation of enfortumab vedotin,
- Treatment-emergent AESIs leading to permanent discontinuation of pembrolizumab,
- Treatment-emergent AESIs leading to dose reduction,
- Treatment-emergent AESIs leading to dose interruption,
- Treatment-emergent AESIs leading to interruption of enfortumab vedotin,
- Treatment-emergent AESIs leading to interruption of pembrolizumab

For selected AESI, time to first onset of AESI, time to first onset of specific grade of AESI (e.g., grade 3 or higher, grade 2 or higher) and time to resolution will be summarized by descriptive statistics by AESI category for each cohort and overall. Time to onset will be summarized at the subject level. Time to resolution will be summarized at the event level.

For other AEs of risk for EV, it will be summarized in the same way as AESI.

For AEOSI, the following tables will be generated:

- Adverse event summary for AEOSI
- Adverse event summary by AEOSI category
- Participants with adverse events of special interest by AEOSI category and preferred term
- Participants with adverse events of special interest by AEOSI category, preferred term, and maximum toxicity grade
- Time to onset of AEOSI
- Summary of concomitant corticosteroid use for AEOSI
- Participants with AEOSI by outcome

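### Time to resolution of enfortumab vedotin AESIs is summarised only among events that resolved, with no planned count of those that did not

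*SAP*

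**What the plan says.** SAP 5.4 Safety Endpoints introduces the variable: "For selected AESI, time to resolution of AESI will be calculated". It then restricts who gets a value. The sentence opens "For treatment-emergent events with an outcome of" and names two outcomes, resolved and resolved with sequelae; for these events "time to resolution will be calculated as time from the event onset date to end date". The unit is the event: "Time to resolution is defined at the event level. AE records that belong to the same event will be linked".

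SAP 6.5.1 Adverse Events sets the summary: "time to resolution will be summarized by descriptive statistics by AESI category for each cohort and overall", and repeats that "Time to resolution will be summarized at the event level". Other AEs of risk for enfortumab vedotin, that is pneumonitis/ILD, are to be summarised as the AESIs are, so the same rule carries over.

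Neither section gives a date or value to an event that is ongoing, or that is cut short by death or data cutoff. The AESI tables listed in 6.5.1 contain no breakdown by outcome. The pembrolizumab list in the same section does: "Participants with AEOSI by outcome".

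**The concern.** A duration computed only for events that have ended selects the short ones. An event that would take a year to resolve enters the summary only if it is watched for a year; one that resolves in two weeks almost always enters. The result therefore mixes how fast events resolve with how long they were observed.

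Unresolved events are to be expected. SAP 6.9.2 treats an event with no stop date as ongoing. Protocol 7.3.3 lets follow-up of an AE end once it has become chronic. SAP 6.8 triggers each cohort's primary analysis once all its subjects could have had 6 months from first dose, so follow-up after the onset of an AESI can be shorter than that.

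Safety and tolerability is a secondary objective, and peripheral neuropathy is a named AESI. A reader will use a time-to-resolution table to judge reversibility. As planned, the table would show a median without showing how many events never reached resolution.

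**Working it through.** The documents state no figure for time to resolution, so there is nothing to reproduce. The check has two parts: whether another passage repairs the omission, and how far the summary could mislead.

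**1. Does another passage repair it?**

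- SAP 6.1 says "For time-to-event endpoints, median survival time will be estimated using Kaplan-Meier method". Section 6.5.1 specifically prescribes descriptive statistics for this variable, and an unresolved event has no time value that could be censored.
- The SAP lists AESIs individually at the end of 6.5.1. A listing is not a summary.
- The SAP revision history (version 3.0) cites the FDA's approach for changing the definition of resolution and for removing time to improvement. It gives no reason for leaving out unresolved events.

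None of these repairs it.

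**2. Direction and possible size**

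If follow-up after onset is independent of time to resolution, the chance of being seen to resolve falls as the time to resolution rises. The resolved-only median therefore cannot exceed the all-event median.

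For size, all inputs are assumptions and none is a document value:

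- m: median time to resolution, in months, among events that would eventually resolve (exponential)
- F: fixed follow-up after onset, in months
- q: share of events that never resolve

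Formulas:

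- Proportion of resolvable events resolved by t: H(t) = 1 − 2^(−t/m)
- Resolved-only median: solve H(t) = 0.5·H(F), giving t = −m·log2[1 − 0.5·H(F)]
- All-event median: solve (1 − q)·H(t) = 0.5, giving t = −m·log2[1 − 0.5/(1 − q)] for q < 0.5; not reached at q = 0.5

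Example with m = 4, F = 6:

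- H(6) = 1 − 2^(−1.5) = 0.646, and half of that is 0.323
- Resolved-only median = −4·log2(0.677) = 2.25
- All-event median with q = 0: 4.00
- All-event median with q = 0.3: −4·log2(1 − 0.714) = 7.23

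| m | F | Resolved by F (q = 0) | Resolved-only median | All-event median, q = 0 | All-event median, q = 30% |
|---|---|---|---|---|---|
| 1 | 12 | 100% | 1.00 | 1.00 | 1.81 |
| 1 | 6 | 98% | 0.98 | 1.00 | 1.81 |
| 2 | 6 | 88% | 1.66 | 2.00 | 3.61 |
| 4 | 6 | 65% | 2.25 | 4.00 | 7.23 |
| 6 | 3 | 29% | 1.37 | 6.00 | 10.84 |
| 6 | 6 | 50% | 2.49 | 6.00 | 10.84 |
| 6 | 12 | 75% | 4.07 | 6.00 | 10.84 |

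Three things follow.

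- For fast resolution with q = 0 the gap vanishes.
- The resolved-only median does not depend on q. It is the same whether every event resolves eventually or half never do, and at q = 50% it stays finite while the all-event median is not reached.
- With the same true median of 6 months, changing follow-up alone from 3 to 6 to 12 months moves the resolved-only median from 1.37 to 2.49 to 4.07. Cohorts with identical recovery would show different figures.

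A simulation of 200,000 events with m = 4 and follow-up uniform on 0 to 12 months agrees. With q = 0, 58% resolve, the resolved-only median is 2.19, and Kaplan-Meier with unresolved events censored gives 3.98. With q = 30%, 41% resolve, and the figures are 2.20 and 7.27. Kaplan-Meier recovers the target here because the simulated censoring is independent and nobody dies.

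**The case against.** The strongest reply is that the summary is openly conditional. The SAP says which events get a duration, and a duration among resolved events is a correct description of those events. Time to response is treated the same way, among responders only and with descriptive statistics (SAP 5.3.1 and 6.4.3.1). This stands: the bias lies in reading the figure as recovery time for all events. But the plan neither labels the figure as conditional nor puts the proportion resolved beside it.

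A reader might infer that unresolved AESIs disappear from the safety report. The documents do not support that. They are absent from this one summary, but they still count in the AESI tables for incidence, relatedness, grade, seriousness, discontinuation, reduction and interruption, and they appear in the listings.

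A reader might also infer that reported recovery times will be wrong by a factor of two or more. The documents do not support that either, because they give no resolution rates. If most AESIs resolve within weeks, the difference is trivial. A later final analysis, once all subjects have left the study (SAP 6.8), also reduces truncation for events still under follow-up.

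Replacing the summary with plain Kaplan-Meier would bring its own problems. Censoring at death treats a competing event as uninformative, which is hard to defend in advanced cancer. One subject may contribute several events, so ordinary intervals would be too narrow. Both points stand and shape the fix.

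Finally, table layouts sit in separate TLF specifications that are not available here, so a denominator may appear there. The SAP itself does not require one.

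**Conclusion.** The point holds as a cheap improvement to a descriptive safety summary. As written, the plan produces resolution times that, read as recovery times, are short for slow-resolving AESIs, and that vary with each cohort's follow-up. It plans no count that would let a reader see this. The direction rests on follow-up being independent of time to resolution. The size is unknown: under the assumptions above it runs from nil (true median 1 month, 12 months of follow-up, every event resolving eventually) to 2.25 against 7.23 months (resolvable-event median 4 months, 6 months of follow-up, 30% never resolving), and it can be larger with shorter follow-up or slower resolution.

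It should not be read as a threat to the trial's conclusions. Time to resolution is added by the SAP; Protocol 9.5.1 does not plan it. The primary endpoint and the interim and final responder boundaries do not use it, and no formal comparison between cohorts is planned.

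**What to change.** Amend SAP 5.4 and 6.5.1, for AESIs and for pneumonitis/ILD:

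1. Report the number and percentage of treatment-emergent AESI events by outcome at data cutoff, per AESI category and cohort, as a counterpart to the outcome table already planned for pembrolizumab AEOSI.
2. Estimate time to resolution over all treatment-emergent AESI events by cumulative incidence. Resolution is the event of interest and death a competing event. Censor ongoing events at the earlier of the last date on which the event's status was known and data cutoff, and define that date in the SAP. Report the proportion resolved at fixed times, and the median if reached. Any confidence intervals should allow for several events per subject.
3. Keep the present summary as supportive, labelled *among resolved events*.

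The cost is SAP wording and a small programming change. The main ingredients (onset date, end date, outcome, death date and cutoff) are already used in planned analyses. The visible consequence is that some reported times will be longer or not reached.

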5.5 Other Endpoints

5.5.1 Cohorts 1 to 8

- Duration of exposure (months)

Duration of exposure = [min (last date of exposure, death, cutoff date) – first dose date +1] / 30.4375

Last date of exposure = (initial dose date of the last cycle + 28 -1)

- Number of cycles

Total number of cycles with non-zero dosing

- Cumulative dose (mg)

Sum of (total dose administered) across all days

Total dose administered on a dosing day (mg) = final concentration (mg/mL) * actual volume administered (mL)

- Planned dose intensity (mg/kg/cycle)

Initial dose of enfortumab vedotin multiplied by planned number of dosing days per cycle.

For example, subject is planned to receive enfortumab vedotin at a dose of 1.25mg/kg on days 1, 8, 15 of each cycle, the planned dose intensity = 1.25mg/kg * 3 = 3.75 mg/kg per cycle.

- Dose intensity (mg/kg/cycle)

$$\frac{\sum_{i=1}^{NC} \sum_{j=1}^3 (TD_{i,j}/W_{i,j})}{(last\ date\ of\ exposure - first\ dose\ date + 1)/28}$$

where, $TD_{i,j}$ is the actual total drug administered at cycle i day j ,

$W_{i,j}$ is the body weight recorded at cycle i day j ,

NC is the number of cycles with non-zero dosing.

If body weight >100 kg, then $W_{i,j}$ = 100 kg. If there is no dose administered on a planned dosing day in a cycle, then $TD_{i,j}$ = 0 mg.

- Relative dose intensity (%)

$$\frac{Dose\ intensity}{Planned\ dose\ intensity} \times 100$$

5.5.2 Cohort 9

For enfortumab vedotin:

- Duration of exposure (months)

Duration of exposure = [min (last date of exposure, death, cutoff date) – first dose date +1] / 30.4375

Last date of exposure = (initial dose date of the last cycle + 21 -1)

- Number of cycles

Total number of cycles with non-zero dosing

- Cumulative dose (mg)

Sum of (total dose administered) across all days

Total dose administered on a dosing day (mg) = final concentration (mg/mL) * actual volume administered (mL)

- Planned dose intensity (mg/kg/cycle)

Initial dose of enfortumab vedotin multiplied by planned number of dosing days per cycle.

For example, subject is planned to receive enfortumab vedotin at a dose of 1.25mg/kg on days 1, 8 of each cycle, the planned dose intensity = 1.25mg/kg * 2 = 2.5 mg/kg per cycle.

- Dose intensity (mg/kg/cycle)

$$\frac{\sum_{i=1}^{NC} \sum_{j=1}^2 (TD_{i,j}/W_{i,j})}{(last\ date\ of\ exposure - first\ dose\ date + 1)/21}$$

where, $TD_{i,j}$ is the actual total drug administered at cycle i day j,

$W_{i,j}$ is the body weight recorded at cycle i day j,

NC is the number of cycles with non-zero dosing.

If body weight >100 kg, then $W_{i,j} = 100$ kg. If there is no dose administered on a planned dosing day in a cycle, then $TD_{i,j} = 0$ mg.

- Relative dose intensity (%)

$$\frac{Dose\ intensity}{Planned\ dose\ intensity} \times 100$$

For pembrolizumab:

- Duration of exposure (months)

Duration of exposure = [min (last date of exposure, death, cutoff date) – first dose date +1] / 30.4375

Last date of exposure = (initial dose date of the last cycle + 21 -1)

- Number of cycles
Total number of cycles with non-zero dosing
- Cumulative dose (mg)
Sum of (total dose administered) across all days

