6.8 Timing of Analyses

Interim analysis for each cohort will be conducted as specified in Section 6.7.

Primary analysis will be conducted for each cohort when all subjects in a cohort have had the opportunity to be followed for at least 6 months after the first dose of study drug. At the time of primary analysis for a cohort other than the last enrolling cohort, all data for that cohort up to data cutoff will be included. For the last enrolling cohort, the following data will be included:

- Efficacy data for the last enrolling cohort up to data cutoff date.
- Non-efficacy data for all subjects from all cohorts up to data cutoff date.

The final analysis of the study will be conducted when all subjects have discontinued from the study.

A Safety Monitoring Committee (SMC) will periodically monitor the study for safety and review study safety data for all cohorts. The details will be provided in the SMC charter.

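### The dose-intensity denominator charges the whole last cycle even when death or data cutoff falls mid-cycle, so a subject given every due dose can be reported below 100% relative dose intensity

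*SAP*

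**What the plan says.** SAP 5.5.1 (cohorts 1 to 8) defines "Last date of exposure = (initial dose date of the last cycle + 28 -1", and 5.5.2 (cohort 9, enfortumab vedotin) defines "Last date of exposure = (initial dose date of the last cycle + 21 -1". Both dates are the nominal end of a full cycle, whatever happened within it.

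Two formulas then use that date differently:

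- Duration of exposure is truncated: "Duration of exposure = [min (last date of exposure, death, cutoff date" are compared, and the earliest is used.
- The dose-intensity denominator is not truncated. In 5.5.1 it is "last\ date\ of\ exposure - first\ dose\ date + 1)/28", and 5.5.2 has the same form with 21. Neither death nor cutoff appears.

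The numerator sums dose per kg over the planned dosing days. "If there is no dose administered on a planned dosing day in a cycle, then" the dose for that day is set to 0 mg. Relative dose intensity is dose intensity divided by planned dose intensity, which is 3.75 mg/kg per cycle in 5.5.1 and 2.5 in 5.5.2.

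SAP 6.3 reports relative dose intensity descriptively on the safety analysis set. SAP 6.7 includes study drug exposure in each cohort's interim package. Under SAP 6.8 a cohort's primary analysis uses data up to cutoff and takes place when all its subjects "have had the opportunity to be followed for at least 6 months after the first dose of study drug". The final analysis follows once all subjects have left the study. I found no rule elsewhere that truncates the denominator or sets aside an incomplete last cycle.

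**The concern.** The SAP recognises in one formula that death and cutoff shorten exposure, and omits this in a formula a few lines later. The numerator stops at death or cutoff, because later doses are not in the data, but the denominator runs on to the end of the cycle. A dose that was never due is then treated like a dose held for toxicity.

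A measure of how fully the regimen was delivered should read 100% when every due dose was given at full strength and on time. Here it reads lower, by an amount that depends on how many subjects die mid-cycle or are on treatment at the snapshot. That mix can differ between cohorts, and between the interim and later analyses of the same cohort, for reasons unrelated to dose holds or reductions.

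**Working it through.** **Inputs (SAP 5.5.1, 5.5.2, 6.8).** Dose 1.25 mg/kg; dosing days 1, 8 and 15 of 28 (cohorts 1 to 8) or 1 and 8 of 21 (cohort 9); ungiven planned doses count as 0 mg; at least 6 months of follow-up opportunity at the primary analysis.

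**The plan's own figures reproduce.** "the planned dose intensity = 1.25mg/kg * 3 = 3.75 mg/kg per cycle" and "the planned dose intensity = 1.25mg/kg * 2 = 2.5 mg/kg per cycle" are both exact. Three complete 28-day cycles give 9 × 1.25 = 11.25 mg/kg over 84/28 = 3 cycles, which is 3.75 per cycle, or 100%.

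**General form.** Take a subject with every due dose given at 1.25 mg/kg and no delay, who ends in cycle k after g doses. In cohorts 1 to 8 the denominator is (28(k − 1) + 27 + 1)/28 = k. Relative dose intensity is therefore (1.25g/k)/3.75 = g/(3k). In cohort 9 it is g/(2k).

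**Death or cutoff after the day 1 dose and before the day 8 dose:**

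| Last cycle | Cohorts 1 to 8 | Cohort 9 |
|---|---|---|
| 1 | 1/3 = 33.3% | 1/2 = 50.0% |
| 2 | 4/6 = 66.7% | 3/4 = 75.0% |
| 3 | 7/9 = 77.8% | 5/6 = 83.3% |

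In cohorts 1 to 8, between the day 8 and day 15 doses, the values are 2/3 = 66.7%, 5/6 = 83.3% and 8/9 = 88.9%. From day 15 (day 8 in cohort 9) the value is 100%.

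**Primary analysis, effect of cutoff only.** Take 6 months as 181 to 184 days; the minimum is the same across that range.

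- Cohorts 1 to 8: study day 181 is cycle 7 day 13 (168 + 13), giving 20/21 = 95.2%. The lowest later point is cycle 8 day 1 (study day 197), giving 22/24 = 91.7%. Cycle 9 day 1 gives 25/27 = 92.6%, and the minimum rises with each further cycle.
- Cohort 9: study day 181 is cycle 9 day 13 (168 + 13), giving 18/18 = 100%. The lowest later point is cycle 10 day 1 (study day 190), giving 19/20 = 95.0%.
- Averaged over all cutoff days in cycle 8 of cohorts 1 to 8: (7 × 22 + 7 × 23 + 14 × 24)/(28 × 24) = 651/672 = 96.9%.

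**Does copying the cap from duration of exposure repair it?** No. For cycle 3 day 2 in cohorts 1 to 8, 7 doses give 8.75 mg/kg and the elapsed time is 56 + 2 = 58 days. Then 8.75/(58/28) = 4.224, and 4.224/3.75 = 112.6%. Doses come early in the cycle, so cutting the time without counting doses due overshoots.

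**The case against.** Three points can be made for the plan.

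- **Low values at the primary analysis.** A reader might infer that subjects ongoing at the primary cutoff could be reported at 67 to 78%. The documents do not support that. With at least 6 months of follow-up opportunity, an on-plan ongoing subject is well past cycle 3, and the floors are 91.7% and 95.0%. This stands in full. Through cutoff, the low values need an interim snapshot.
- **Deaths are a convention.** The formula charges the whole last cycle after any stop. One may argue that a dose missed because the subject died is rightly undelivered. This stands in part: either convention can be defended if stated. But the SAP truncates at death in duration of exposure and not here, without saying that the difference is intended. The argument also gives no support to the cutoff case, where the subject is alive and the next dose is simply not due.
- **Importance.** Relative dose intensity is one of six descriptive exposure statistics in SAP 6.3. It sits beside counts of dose adjustment, reduction and interruption, and the adverse-event tables cover discontinuation, reduction and interruption. No formal comparison between cohorts is planned. This stands, and it limits the weight of the point without making the formula right.

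**Conclusion.** The formula is wrong as written, and the consequence is minor. Relative dose intensity is understated for a subject whose last cycle is cut by death or cutoff before its last planned dose. The understatement is large only in early cycles, through an interim snapshot or an early-cycle death. The death route is open at any analysis; the cutoff route is small at the primary analysis and closes at the final one.

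The figures assume full dosing on the nominal days with no cycle delay. The interim figures also assume that exposure is summarised on the safety analysis set, as SAP 6.3 states, and that some subjects are then in cycles 1 to 3. The documents do not say how many subjects would be affected, so no effect on a cohort mean or median can be given.

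A reader might go further and infer that the planned intensities are miscalculated, or that conclusions on efficacy are at risk. Neither follows: 3.75 and 2.5 are correct, and no efficacy endpoint or BOP2 boundary uses dose intensity.

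**What to change.** In SAP 5.5.1 and 5.5.2, define relative dose intensity for enfortumab vedotin as actual dose (mg/kg) divided by expected dose (mg/kg), where

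expected dose = initial dose × [planned doses per cycle × (day 1 of last cycle − first dose date)/cycle length + number of planned dosing days of the last cycle on or before min(last date of exposure, death, cutoff)].

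Checks, cohorts 1 to 8:

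- On plan, cutoff on cycle 3 day 2: expected 1.25 × (3 × 56/28 + 1) = 8.75, given 8.75, so 100%.
- Cycle 2 started 7 days late and completed: expected 1.25 × (3 × 35/28 + 3) = 8.4375, given 7.5, so 88.9%. The present formula gives the same (7.5/2.25/3.75), so delays are still penalised.
- Treatment stopped after cycle 3 day 1, with the subject alive and observed past day 15: expected 1.25 × (6 + 3) = 11.25, given 8.75, so 77.8%, as now. A fully observed discontinuation is still charged the whole cycle.

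Two simpler repairs should be avoided. Capping only the existing denominator overshoots 100%, as shown above. Dropping the incomplete last cycle is undefined for a subject who ends in cycle 1, and it discards real omissions: if days 8 and 15 are held for toxicity and cutoff falls on day 25, both held doses disappear from the calculation.

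If the sponsor does intend to charge the full cycle after death, one sentence saying so would suffice for that case; the cutoff case still needs the change. The cost is one formula in two sections and a small program change, with no new data.
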